9.3 Recording and Documentation of AEs

At each contact with the subject, designated study staff must seek information as to discomforts or adverse experiences by specific questioning and, as appropriate, by examination. At study visits, safety laboratory evaluations will also be performed to identify any laboratory AEs. All side effects will be reported to the PI and/or physician co-investigators on a daily basis and toxicity laboratory results will be reviewed in real time. Information about AEs to be recorded includes event description, time of onset, investigator assessment of severity, relationship to study agent(s)/Intervention(s), and time of resolution/stabilization of the event. All AEs occurring during the study period (from time of consent signing to 3 months after the last study visit) must be documented appropriately regardless of relationship to study products or procedures. Information on all AEs will be promptly recorded in the source document and also in the appropriate AE module of the case report form (CRF).

Any medical condition that is present at the time that the participant is screened should be considered as baseline and not recorded as an AE. However, if the condition deteriorates at any time during the study it should be recorded and reported as an AE. Changes in the severity of an AE should be documented to allow an assessment of the duration of the event at each level of intensity to be performed. Adverse events characterized as intermittent require documentation of the onset and duration of each episode. Changes in the assessment of relationship to the study agent(s)/interventions should also be clearly documented.

9.3.1 Scales Used to Grade Severity of Adverse Events

The grading system for severity of AEs is located in the DAIDS Table for Grading the Severity of Adult and Pediatric Adverse Events, Version 1.0, December 2004 (Clarification August 2009), which can be found on the DAIDS RSC Web Site: <http://rsc.tech-res.com/safetyandpharmacovigilance/>.

9.3.2 Scales Used to Attribute Adverse Events

The Principal Investigator will assess the relationship of all AEs to any drug or study procedure according to the following criteria:

1. Definitely Related: There is clear evidence to suggest a causal relationship, and other possible contributing factors can be ruled out. The clinical event, including an abnormal laboratory test result, occurs in a plausible time relationship to study agent/intervention administration and cannot be explained by concurrent disease or other drugs or chemicals. The response to withdrawal of the study agent/intervention (de-challenge) should be clinically plausible. The event must be pharmacologically or phenomenologically definitive, with use of a satisfactory re-challenge procedure if necessary.
2. Probably Related: There is evidence to suggest a causal relationship, and the influence of other factors is unlikely. The clinical event, including an abnormal laboratory test result, occurs within a reasonable time sequence to administration of the study agent/intervention, is unlikely to be attributed to concurrent disease or other drugs or chemicals, and follows a clinically reasonable response on withdrawal (de-challenge). Re-challenge information is not required to fulfill this definition.
3. Possibly Related: There is some evidence to suggest a causal relationship (e.g., the event occurred within a reasonable time after administration of the trial medication). However, the influence of other factors may have contributed to the event (e.g., the subject's clinical condition or other concomitant events). Although an adverse drug event may rate only as "possible" soon after discovery, it can be flagged as requiring more information and later be upgraded to "probable" or "certain" as appropriate.
4. Unlikely: A clinical event, including an abnormal laboratory test result, whose temporal relationship to study agent/intervention administration makes a causal relationship improbable (e.g., the event did

not occur within a reasonable time after administration of the trial medication) and in which other drugs or chemicals or underlying disease provides plausible explanations (e.g., the subject's clinical condition or other concomitant treatments).

5. Not Related: The AE is completely independent of study agent/intervention administration, and/or evidence exists that the event is definitely related to another etiology. There must be an alternative and definitive etiology documented by the clinician.

9.3.3 Analysis/Management

The clinical course of each event will be followed until resolution, stabilization, or until it has been determined that the study treatment or participation is not the cause. Any measures taken or follow-up results are to be recorded in the study file. In addition, any clinically meaningful incidental findings from colonoscopies or lymph node biopsies will be promptly communicated to the study participant's primary care provider by fax, e-mail, letter, and/or telephone call. Documentation of appropriate follow up and reporting of all AEs will consist of written telephone contact reports, faxes, e-mail messages, and/or letters, which will be kept in the study files. SAEs that are still ongoing at the end of the study period must be followed to determine the final outcome. Study physicians will be responsible for evaluating subjects in the case of AEs. Study physicians and study staff are responsible for communicating to subjects information arising from the study (on harm or benefit, for example), or from other research on the same topic that could affect subjects' willingness to continue in the study.

9.4 Reporting Procedures

9.4.1 AEs to be Reported

The following AEs will be promptly reported within three reporting days to the DSMB and the DAIDS medical monitor:

- all cancers, all autoimmune diseases, all fetal losses associated with an AE,
- all overdoses associated with an AE, and
- any definitely related, unexpected, and serious adverse events (SUSARS).

Other AEs or unanticipated problems will be reported to the IRB and DSMB within their reporting timelines (such as annual review or if prompt reporting is required, within the urgent reporting timeline requirements).

At the time of the initial report, the following information should be provided:

- Study identifier,
- Subject number,
- A description of the event,
- Date of onset,
- Current status,
- Whether study treatment was discontinued,
- The reason why the event is classified as serious, and
- Investigator assessment of the association between the event and study treatment.

Copies of each report and documentation of applicable IRB notification and receipt will be kept in the Clinical Investigator's binder. All reportable AEs will be followed until satisfactory resolution or until the PI or Sub-investigator deems the event to be chronic or the participant to be stable. If a previous SAE that was not initially deemed reportable under expedited reporting criteria is later found to fit the criteria

for reporting, the PI will submit the SAE in a written report as soon as possible. The full list of adverse events and complications will be reviewed by the IRB and DSMB on an annual basis.

Table: Expedited Reporting to IRB, DSMB and DAIDS

Expedited Reporting to Whom	Criteria for Reporting	Timeframe	Submission Format
IRB	Unanticipated death of a locally enrolled subject(s); New or increased risk; Any adverse event that requires a change to the protocol or consent form; Unanticipated problems; Refer to the IRB website for complete details on required reporting criteria.	5 working days	Local IRB's standard reporting form
DSMB	1) SUSARS 2) all cancers, all autoimmune diseases, all fetal losses associated with an AE, and all overdoses associated with an AE 3) Unanticipated death of locally enrolled subject(s)	3 reporting days (defined as M-F, including holidays)	Submit AE/SAE CRF, and IRB Report form, if available.
DAIDS	1) SUSARS 2) all cancers, all autoimmune diseases, all fetal losses associated with an AE, and all overdoses associated with an AE 3) Grade 3 and 4 AEs that are attributed to study procedures (graded as per section 9.3.1 above)	3 reporting days (defined as M-F, including holidays)	Submit SAE/AE CRF to DAIDS medical officer.

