9.1.3 Definition of a Suspected Unexpected Serious Adverse Reaction (SUSAR)

An AE that is:

- Serious (i.e., an SAE),
- Related (i.e., there is a reasonable possibility that the AE may be related to the study product), and
- Unexpected (i.e., an AE whose nature or severity [intensity] is not consistent with the applicable product information found in an investigator's brochure, a package insert or a summary of agent characteristics).

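### The 9.4.1 bullet limits three-day SUSAR reporting to definitely related events, in conflict with the SUSAR definition in 9.1.3, the table in 9.4.1 and section 9.4.2

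*Combined protocol and SAP*

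**What the plan says.** Four places in the protocol bear on this point.

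- **Definition (9.1.3).** A SUSAR is serious, unexpected and related, and the relatedness element reads "Related (i.e., there is a reasonable possibility that the AE may be related to the study product".
- **Attribution scale (9.3.2).** There are five levels: definitely, probably, possibly, unlikely and not related. The top level requires that "There is clear evidence to suggest a causal relationship, and other possible contributing factors can be ruled out", together with a clinically plausible response to withdrawal and a re-challenge if needed. The next two are defined separately: "Probably Related: There is evidence to suggest a causal relationship, and the influence of other factors is unlikely" and "Possibly Related: There is some evidence to suggest a causal relationship".
- **Reporting list and table (9.4.1).** The list opens with "The following AEs will be promptly reported within three reporting days to the DSMB and the DAIDS medical monitor", and its last bullet is "any definitely related, unexpected, and serious adverse events (SUSARS". AEs outside the list go to the IRB and DSMB on those bodies' own schedules; annual review is the example given, with an urgent track where prompt reporting is required. DAIDS is not named in that sentence. The table that follows gives SUSARs, with no further qualifier, three reporting days for both the DSMB and DAIDS.
- **Expedited reporting to DAIDS (9.4.2).** SUSARs are again listed without a qualifier, and the timeline is taken from the DAIDS EAE Manual.

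**The concern.** The same label, SUSAR, carries two relatedness thresholds. Definitely is not loose wording in this protocol: it is the highest of five defined levels. It is also hard to reach within a few days of an event. Participants take ART alongside study drug, investigators are blinded, and the top level turns on ruling out other causes and on the response to withdrawal. Section 9.3.2 itself notes that an event may be rated only possible soon after discovery and be upgraded later.

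At stake is whether the DSMB and the DAIDS medical monitor hear quickly of an unexpected serious reaction. Section 9.7.1 lets review of serious, unexpected and related events by those parties lead to suspension of study agent, and it does not ask that they be definitely related. Section 2.2 says that interactions between losartan and ARVs have not been extensively studied. A reporting gate narrower than the definition would restrict what feeds that review.

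**Working it through.** No arithmetic applies. The check takes an unexpected SAE at each level of the 9.3.2 scale and asks whether it must be reported in three reporting days, first under the 9.4.1 bullet and then under the 9.4.1 table read with the 9.1.3 definition.

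| 9.3.2 level | On the three-day list by the 9.4.1 bullet? | SUSAR under 9.1.3, so three days by the 9.4.1 table? | Agree? |
|---|---|---|---|
| Definitely | Yes | Yes | Yes |
| Probably | No | Yes, on any reading | **No** |
| Possibly | No | Yes, by inference | **No** |
| Unlikely | No | No | Yes |
| Not related | No | No | Yes |

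The readings disagree at 2 of 5 levels, which are 2 of the 3 levels that express a relationship.

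**Probably.** Evidence of causation with other factors unlikely is more than a reasonable possibility, so this row needs no assumption.

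**Possibly.** Section 9.1.3 does not map its threshold to the scale, so this row is an inference. Section 9.2 supports it: for unanticipated problems, it explains possibly related as a reasonable possibility of causation.

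**Where the two middle rows go under the bullet.** They become other AEs, sent to the IRB and DSMB on their own schedules. Each of the following routes could still bring prompt notice:

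1. *Unanticipated problem (9.2).* The investigator applies this test to every AE. It needs the event to be unexpected, at least possibly related, and suggestive of greater risk than previously recognised. If met, it is reported promptly to the IRB and DSMB; the table gives the IRB 5 working days. An SAE in the middle rows meets the first two conditions but not necessarily the third.
2. *Unanticipated death.* The table gives the DSMB 3 reporting days and the IRB 5 working days, with no relatedness condition.
3. *Grade 3 or 4 AE attributed to study procedures.* DAIDS receives this in 3 reporting days. It does not cover drug-related events.
4. *Events listed in their own right.* Cancers, autoimmune diseases, and fetal losses and overdoses associated with an AE are on the three-day list whatever their relatedness.
5. *Later upgrade.* An SAE found afterwards to meet the expedited criteria is reported in writing as soon as possible.

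**What is left.** Outside the separately listed categories, no route covers every non-fatal, drug-related, unexpected SAE rated possibly or probably related that is not judged an unanticipated problem. Under the bullet it may wait until the annual review of AEs by the IRB and DSMB, unless the urgent track is invoked.

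**The case against.** The strongest reply is that the protocol already contains the wider duty. Section 9.1.3 is where SUSAR is defined, and the table and 9.4.2 use the term unqualified, so one bullet is the outlier and a careful site would follow the table. This is sound as to which reading has more support in the text. It does not remove the conflict: bullet and table sit in the same section, both say three days, and a site acting on the bullet is following the protocol as written.

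The reply also correctly limits the consequence. A reader might infer any of the following, and the documents support none of them:

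- *Most SUSARs would be reported late, by up to a year.* No event rate or split across attribution levels is given. Annual review is an outer limit, because the same sentence in 9.4.1 provides an urgent track and 9.2 a prompt one.
- *Fatal events would escape the DSMB.* Unanticipated deaths have their own three-day line in the DSMB row.
- *A serious renal event shows the gap.* Worsening renal function is a listed losartan risk in 2.4.1, and 9.1.3 judges unexpectedness against product information. Such an event is a SUSAR only if its nature or severity departs from that information.
- *The final safety data would be incomplete.* Section 9.3 requires all AEs to be recorded whatever their relationship to study product.
- *Drug interactions would go unwatched.* Section 7.2 provides drug-level analysis in semi real time, and 9.3 real-time review of toxicity laboratory results.

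For DAIDS, 9.4.2 takes definitions and timeline from the EAE Manual, and 9.2 invokes the DAIDS Critical Event Policy. Neither document was available for this review, and either may narrow the gap further.

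**Conclusion.** The point stands as an internal inconsistency in safety reporting, of limited reach. The bullet in 9.4.1 sets a higher relatedness threshold than 9.1.3, the table in 9.4.1 and section 9.4.2. The two thresholds give different instructions for unexpected SAEs rated probably related, which needs no assumption, and possibly related, which rests on carrying the usage in 9.2 over to 9.1.3.

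The practical gap is the residual class identified above, and it opens only where staff act on the bullet rather than the table. For such an event the delay is at most until annual review. How often it would arise cannot be estimated from the documents. Randomisation, endpoints and the efficacy analysis are untouched. The correction is still worth making, because for these two levels the bullet asks for less prompt reporting than the definition and table do, and the remedy is very cheap.

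**What to change.** In 9.4.1, replace the words "any definitely related, unexpected, and serious adverse events (SUSARS" and their closing bracket with: SUSARs as defined in section 9.1.3. In 9.1.3, state which levels of the 9.3.2 scale count as a reasonable possibility, so that the definition, the list, the table and 9.4.2 share one threshold.

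The cost is one or two lines of protocol wording and possibly a few more three-day reports on existing forms. No assessment, visit or analysis changes.

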9.4.2 Expedited Adverse Event (EAE) Reporting to DAIDS

EAE Reporting to DAIDS

The definitions of AEs requiring expedited reporting are outlined in Version 2.0 of the DAIDS EAE Manual, which is available on the DAIDS RSC website at <http://rsc.tech-res.com/safetyandpharmacovigilance/>.

EAE Reporting Requirements for the Study

The events for which expedited reporting is required include Suspected, Unexpected Serious Adverse reactions (SUSARs). In addition to the EAE Reporting Category identified above, other AEs that will be reported in an expedited manner include all cancers, all autoimmune diseases, all fetal losses associated with an AE, all overdoses associated with an AE and all Grade 3 and 4 AEs that are attributed to study procedures (graded as per section 9.3.1 above).

The timeline for reporting of expedited events to the DAIDS medical officer is as defined in the DAIDS EAE manual.

The study agents for which expedited reporting is required are losartan, placebo for losartan, Gardasil, darunavir, and elvitegravir/cobicistat/emtricitabine/tenofovir.

Grading Severity of EAEs

The grading table used for this study is the DAIDS Table for Grading the Severity of Adult and Pediatric Adverse Events, Version 1.0, December 2004 (Clarification August 2009), which can be found on the DAIDS RSC Web Site: <http://rsc.tech-res.com/safetyandpharmacovigilance/>.

Expedited AE Reporting Period

The reporting period will be from the time the subject starts the study drug until the end of the study follow up for that participant. After the protocol-defined AE reporting period, only SUSARs as defined in Version 2.0 of the EAE Manual will be reported to the IRB and DSMB if the study staff become aware of the events on a passive basis (from publicly available information). A copy of these reports will also be sent to the DAIDS Medical Officer.

9.5 Reporting a Pregnancy

Pregnant women are not eligible to participate in the study. Women are counseled regarding prevention of pregnancy and encouraged to make every effort to avoid pregnancy during study participation. In addition to the screening and baseline visits, pregnancy testing will occur every 3 months and anytime during follow up when the woman or investigator suspects pregnancy. If a study participant becomes pregnant during study participation, no further doses of losartan or Gardasil will be given and no additional study procedures will be performed. Basic information about the pregnancy will be recorded on the "Pregnancy" CRF and permission to record survival data for her until the end of the pregnancy and of the baby at birth will be requested. If there are complications during the pregnancy, the complications are recorded as AEs in the usual way. The participant is asked to report outcome of the pregnancy. If there is a congenital anomaly in the infant, this is recorded as a serious adverse event (SAE) in the data forms for the mother (i.e., the study participant).

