2.4 Potential Risks and Benefits

2.4.1 Potential Risks

Potential risks of study procedures (venipuncture, inguinal LN biopsy, and colonoscopy with GALT biopsies) are detailed in Section 7.1 and in consent forms. According to the Losartan package insert, the most severe risks of losartan use include teratogenicity in the setting of pregnancy, hypersensitivity, symptomatic hypotension, worsening of renal function, and electrolyte abnormalities. The most common side effects of losartan include fatigue, weakness, diarrhea, chest pain, tachycardia and anemia.

Subjects will be rigorously screened to ensure that they are at low risk for complications due to losartan and they will be monitored closely for side effects and signs of toxicity. The most common side effects of Gardasil include headache, fever, nausea, dizziness and injection site reactions. Severe reactions, including hypersensitivity, are rare. The most common side effects of Stribild are new onset or worsening of renal impairment, bone effects, fat distribution and immune reconstitution syndrome. The most common side effects of Stribild include nausea, diarrhea, abnormal dreams, headache, rash, fatigue, dizziness, insomnia, flatulence, somnolence, ocular icterus and jaundice. The most common side effects of Prezista are drug –induced hepatitis, skin reactions ranging from mild to severe, use with caution with a known sulfonamide allergy, new onset diabetes or hyperglycemia, redistribution/accumulation of body fat or immune reconstitution syndrome and subjects with hemophilia may develop increased bleeding events, The most common side effects of Prezista include diarrhea, nausea, rash, headache, abdominal pain and vomiting.

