7.2 Plan to Minimize Risks to Subjects

All investigators and study staff have completed required training regarding human subject protections. Study staff will comply with all related regulations and laws, included, but not limited to 45 CFR 46 and 21 CFR 50, 56 (FDA version), and HIPAA Privacy Regulations. Study will be conducted in accordance with US and international standards for good clinical practices, applicable regulations, and institutional research policies and procedures.

Subjects will be rigorously screened against inclusion/exclusion criteria to ensure that their participation is safe. All staff members responsible for taking a medical history that could potentially make the participant uncomfortable have been specifically trained for how to do this in a sensitive manner. Only qualified study or clinic staff or physicians will draw blood to minimize risks. Pregnancy testing will be performed at screening, baseline, every 3 months, and anytime during follow up when the woman or investigator suspects pregnancy. In addition, study staff will stress the importance of adherence to contraceptives in order to minimize risks related to unintended fetal exposure. Subjects will be closely observed for systemic adverse events and toxicity related to the study drug on a routine basis through interviews, clinical assessment (including measuring vital signs and physical exam), and monitoring of renal function, liver function, and hematologic panel. All lymph node biopsies will be performed by either [name], [name], or [name] who have performed >400 LN biopsies in the research setting without significant complications. All colonoscopies will be performed by [name] who has performed >300 colonoscopies and biopsies in related HIV studies in the past without any complications. Subjects will be monitored after biopsy procedures for at least 4 hours by study staff trained in managing postoperative patients. They will be monitored for at least 30 minutes after HPV vaccine administration to ensure that they tolerate the vaccine without difficulty.

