8.1.7 Month 23 Visit

Subjects will be seen for clinical assessment (interval history and targeted exam), review of drug adherence, refill of study drug, and blood draw for CBC, CMP, CD4, VL, plasma, serum and PBMCs. In addition, the first dose of Gardasil (human papillomavirus recombinant vaccine) will be administered. Subjects will remain in the MCRU for 30 minutes after administration for monitoring.

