8.2 Schedule of Events for HIV Infected Subjects

Table 1. Protocol summary for HIV infected subjects:

	Screen	Day 0	Day 14	Month 1	Months 3, 6, 9, 15, 18, 21, 27	Month 12	Month 23	Month 25	Month 29.5	Month 30
Medical history	X	X								
Interval medical history			X	X	X	X	X	X	X	X
Physical Exam ¹	X	X	X	X	X	X	X	X	X	X
Adherence assessment and counseling		X	X	X	X	X	X	X	X	X
Pregnancy test ²	X	X		X	X	X		X	X	
HCV Ab	X									
CMP	X	X	X	X	X	X	X		X	X
CBC w diff	X	X	X	X	X	X	X		X	X
CD4 count	X	X		X	X	X	X		X	X
HIV viral load	X	X		X	X	X	X		X	X
Serum ³		X		X	X	X	X	X	X	X
Plasma /PBMCs ⁴		X		X	X	X	X	X	X	X
Additional PBMCs ⁵		X				X				X
Biopsies ⁶		X				X				X
HPV vaccine ⁷							X	X	X	
PK assessment				X ⁸	X ⁹	X ⁹		X ⁹		X ¹⁰

1. At screening, a full physical exam will be performed (described above). At subsequent visits, a targeted exam will be performed.
2. Women of childbearing age must have a negative pregnancy test prior to enrollment. Pregnancy testing will also occur roughly every 3 months during follow up and additionally if the subject or investigator suspects pregnancy.
3. Serum will be used to determine levels of IL-7 and TGF-beta.
4. Plasma will be used to determine levels of cytokines and markers of inflammation. PBMCs will be used in flow cytometry and intracellular cytokine staining.
5. Additional blood will be obtained from subjects enrolled in the two-photon microscopy sub-study.
6. Inguinal LN biopsy and colonoscopy with sampling of ileal and rectal tissues.
7. Human papillomavirus quadrivalent vaccine (Gardasil) will be administered at 3 time points per recommended vaccine schedule and immune response will be assessed at month 30.
8. Intensive 24-hour PK assessment will be performed at month 1 visit.
9. Plasma and intracellular PBMC concentration of losartan and ARVs will be determined approximately every quarter.
10. Plasma and intracellular PBMC concentration of losartan and ARVs PLUS concentrations in LN and GALT will be determined at month 30.

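### Table 1 leaves a 4-month gap between pregnancy tests (month 21 to month 25), while sections 7.2 and 9.5 promise a test every 3 months

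*Combined protocol and SAP*

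**What the plan says.** The protocol gives the frequency of pregnancy testing for HIV-infected women in three places.

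- Section 7.2 (Plan to Minimize Risks to Subjects): "Pregnancy testing will be performed at screening, baseline, every 3 months, and anytime during follow up when the woman or investigator suspects pregnancy".
- Section 9.5 (Reporting a Pregnancy): "In addition to the screening and baseline visits, pregnancy testing will occur every 3 months", with testing on suspicion added.
- Section 8.2, Table 1, footnote 2: "Pregnancy testing will also occur roughly every 3 months during follow up", also with testing on suspicion added.

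The pregnancy-test row of Table 1 is marked at screening, day 0, month 1, the grouped column for "Months 3, 6, 9, 15, 18, 21, 27", month 12, month 25 and month 29.5. It is blank at day 14, month 23 and month 30.

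The month-23 visit (section 8.1.7) includes "review of drug adherence, refill of study drug, and blood draw for CBC, CMP, CD4, VL, plasma, serum and PBMCs", and at the same visit "the first dose of Gardasil (human papillomavirus recombinant vaccine) will be administered". Section 2.4.1 says that "the most severe risks of losartan use include teratogenicity in the setting of pregnancy".

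**The concern.** Sections 7.2 and 9.5 give a plain 3-month frequency, and section 7.2 presents it as a safeguard against fetal exposure. Table 1 is what site staff will follow, because the narrative visit descriptions in section 8.1 name a pregnancy test only at screening. If the table spaces two tests more than 3 months apart, staff who follow it exactly will miss the stated frequency for every woman of childbearing age who reaches month 25.

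What is at stake is the time a pregnancy could go undetected on a drug described as teratogenic. Section 9.5 stops both losartan and Gardasil once pregnancy is known. Month 23 is a visit where study drug is resupplied and the first vaccine dose is given, so a missed pregnancy there would mean further exposure to both for a woman on losartan.

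**Working it through.** **Is the table read correctly?** The text extraction could have shifted columns, so two other rows were compared with the visit descriptions.

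- The metabolic panel row is blank at month 25 and marked at month 23. Section 8.1.8 lists no metabolic panel at month 25, and section 8.1.7 lists one at month 23.
- The vaccine row is marked at months 23, 25 and 29.5, as section 7.1.5 states.

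The columns line up, so the blank at month 23 in the pregnancy row is genuine.

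**Scheduled tests from day 0, in months:** 0, 1, 3, 6, 9, 12, 15, 18, 21, 25, 27, 29.5. That is 12 tests and 11 intervals.

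| From | To | Interval (months) |
|---|---|---|
| 0 | 1 | 1 |
| 1 | 3 | 2 |
| 3 | 6 | 3 |
| 6 | 9 | 3 |
| 9 | 12 | 3 |
| 12 | 15 | 3 |
| 15 | 18 | 3 |
| 18 | 21 | 3 |
| **21** | **25** | **4** |
| 25 | 27 | 2 |
| 27 | 29.5 | 2.5 |

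The mean interval is 29.5 / 11 = 2.68 months. The maximum is 4 months, and exactly one interval exceeds 3. The stated frequency therefore holds on average but not for the interval from month 21 to month 25. Month 23 is the only scheduled visit inside it.

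**Excess over the stated frequency:** 25 − 21 = 4 months, and 4 − 3 = 1 month.

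**With a test added at month 23:** 23 − 21 = 2 and 25 − 23 = 2. There are then 12 intervals with mean 29.5 / 12 = 2.46 months and maximum 3 months.

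**How many women?** The documents do not say. As an assumption, take the 83% male share that section 5.1 gives for people living with HIV/AIDS in Minnesota, which that section expects the sample to resemble. Women are then 17%.

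- Of 50 completers: 0.17 × 50 = 8.5 women, and 8.5 / 2 = 4.25 on losartan.
- Of 63 enrolled: 0.17 × 63 = 10.7 women, and 10.7 / 2 = 5.4 on losartan.

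These figures count all women. Those of childbearing age are fewer, and no age split is given.

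**The case against.** The strongest reply is that footnote 2 sits on this very row and describes the frequency as approximate. Read that way, the table agrees with itself, and all that is missing is one adverb in two narrative sentences. It can also be argued that a frequency is not a maximum gap. Neither section sets a cap or a visit window, and on average women are tested more often than quarterly.

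The pattern may be deliberate too. There is no month-24 visit, and the pharmacokinetic row follows the same course: marked in the month-21 group, blank at month 23, marked at month 25. Month 25 may simply stand in for the quarterly visit.

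Finally, other safeguards are in place. Section 5.2 requires effective contraception and does not accept condoms as the sole method. Section 7.1.3 provides contraceptive adherence counselling at each visit. The month-23 visit includes an interval history and an examination, and testing on suspicion is available throughout.

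Much of this stands. It makes the gap small and probably a by-product of fitting tests to vaccine visits. The silence of section 8.1.7 about a test proves little, since no follow-up visit description mentions one. No section requires a test before vaccination. But the footnote does not qualify sections 7.2 and 9.5, so the protocol still states its frequency in two ways. Those sections also offer scheduled testing in addition to testing on suspicion, so the one does not replace the other.

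**Conclusion.** The concern holds, at the lowest level of importance. One of the 11 scheduled intervals is 4 months against a stated 3, so a pregnancy starting soon after the month-21 test could go up to one month longer before a scheduled test than sections 7.2 and 9.5 imply. This rests on reading the stated frequency as applying to each interval and on staff testing only where Table 1 is marked.

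The number of women affected cannot be determined. Under the assumed 17% share, about 4 to 5 women would be on losartan, before restricting to those of childbearing age. There is no consequence for endpoints, sample size, power or analysis.

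**What to change.** Mark a pregnancy test at month 23 in Table 1. The visit already exists, with a blood draw and a drug refill, and Table 1 then meets the frequency in sections 7.2 and 9.5 through month 29.5. A side benefit is a test at the visit where the first Gardasil dose is given, as Table 1 already schedules for the other two doses.

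The cost is one table cell and one urine test per woman of childbearing age.

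Inserting the footnote's qualifier into sections 7.2 and 9.5 would also reconcile the wording. It would do so by loosening a fetal-safety commitment to save a single test, so the added test is the better choice.
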